### 8.1.2 Relationship Categorization

A physician/investigator must make the assessment of relationship to investigational product for each AE. The investigator should decide whether, in his or her medical judgment, there is a reasonable possibility that the event may have been caused by the investigational product. If there is no valid reason for suggesting a relationship, then the AE should be classified as “not related.” Otherwise, if there is any valid reason, even if undetermined or untested, for suspecting a possible cause-and-effect relationship between the investigational product and the occurrence of the AE, then the AE should be considered “related.” The causality assessment must be documented in the source document.

The following additional guidance may be helpful:

Term	Relationship Definition
Related	The temporal relationship between the event and the administration of the investigational product is compelling and/or follows a known or suspected response pattern to that product, and the event cannot be explained by the subject’s medical condition, other therapies, or accident.
Not Related	The event can be readily explained by other factors such as the subject’s underlying medical condition, concomitant therapy, or accident and no plausible temporal or biologic relationship exists between the investigational product and the event.

### 8.1.3 Adverse Events of Special Interest

Adverse events of special interest will be captured and monitored during this study. Investigators will report all AESIs to the sponsor, regardless of causality, using the same timelines as described for SAE reporting (see Section 8.2.2). The following describe the AESIs and the criteria for reporting AESIs.

[figure not shown]
### 8.1.3.1 Hypersensitivity

Potential hypersensitivity, serum sickness, vasculitis, and Arthus reactions to ontamalimab will be regarded as AESIs. These events must be reported on Shire “Clinical Study SAE and Nonserious AE as Required by the Protocol Form” and within the time frame mandated for SAEs (see Section 8.2.2).

It is well known that the administration of foreign proteins can cause immune responses including hypersensitivity reactions such as anaphylaxis and serum sickness. Other immune responses to foreign proteins include the development of ADAs and NABs.

Monoclonal antibodies have been used in human therapeutics since the 1980s. The first monoclonal antibody approved for human use (ORTHOCLONE OKT3®), was a murine protein which caused rapid production of NABs. Since then, much effort has been expended to reduce the immunogenicity of these useful therapeutic proteins by reducing the extent of “foreignness” from chimeric antibodies such as infliximab, to humanized antibodies such as vedolizumab, and finally to fully human antibodies such as adalimumab and ontamalimab (Isabwe et al., 2018) (see Figure 4).

**Figure 4 Potential Immunogenicity of Therapeutic Monoclonal Antibodies**

Ontamalimab is a fully human antibody of the immunoglobulin G2 subclass. In Phase 1 and Phase 2 clinical trials of ontamalimab, in which over 700 subjects were treated for up to 3 years, there has been no case of anaphylaxis. There have been 2 reported cases of drug hypersensitivity: serum sickness attributed to concomitant administration of penicillin; and a reaction characterized by dyspnea, facial erythema, and chest pain with onset 2 days after administration of the fifth dose of ontamalimab. The latter event mimicked a reaction that the subject had previously experienced after 4 doses of infliximab. In addition, low titer activity has been observed in ADA assays, including pretreatment samples and placebo-treated subjects, and no subject has had a 2-fold or greater increase in ADA titer. Analysis of PK and clinical

parameters has shown no difference between subjects whose ADA assays results are positive as compared with those whose are negative.

Nonetheless the possibility of a hypersensitivity reaction occurring after drug exposure cannot be fully ruled out. The reactions of concern are Type I (anaphylaxis) and Type III (immune complex) reactions. The clinical presentation of anaphylactic reactions is described in [Table 6](#).

**Table 6 Clinical Criteria for Diagnosing Anaphylaxis (Type I Hypersensitivity)**

**Anaphylaxis is highly likely when below criterion and at least any one of the following criteria a and b are fulfilled:**

Acute onset of an illness (minutes to several hours) with involvement of the skin, mucosal tissue, or both (eg, generalized hives, pruritus or flushing, swollen lips-tongue-uvula)

*AND AT LEAST ONE OF THE FOLLOWING*

- a) Respiratory compromise (eg, dyspnea, wheeze-bronchospasm, stridor, reduced PEF, hypoxemia)
- b) Reduced BPa or associated symptoms of end-organ dysfunction (eg, hypotonia [collapse], syncope, incontinence)

BP=blood pressure; PEF=peak expiratory flow

a Low systolic BP for children is defined as less than 90 mmHg from 11 to 17 years.

Source: Adapted from [Sampson et al., 2006](#).

Type III hypersensitivity responses, including those mediated by immune complexes and T cells (delayed hypersensitivity responses in the older literature), are relatively rare with respect to therapeutic protein products and a high degree of clinical suspicion is necessary for the diagnosis (Center for Drug Evaluation and Research – Guidance for industry: Immunogenicity assessment for therapeutic protein products, 2014). Type III hypersensitivity reactions involve the formation of biologic/ADA immune complexes in the circulation which, when present in the correct stoichiometric ratio, become deposited in tissues. Once immune complexes are deposited, they can elicit complement activation and inflammation, leading to tissue damage. When immune complexes are deposited in tissues, they tend to localize in small postcapillary venules where there is loss of laminar blood flow, in sites of ultrafiltration where there is high pressure and fenestrated endothelium (eg, choroid plexus, ciliary body, synovium, and glomeruli), in sites of turbulent blood flow (eg, coronary artery branches off aorta, aortic bifurcations, and cardiac valve leaflets), and in renal glomerular endothelium.

Signs and symptoms of immune complex deposition typically have onset 1 to 3 weeks after exposure ([Warrington et al., 2018](#)) usually improving in 7 to 10 days, with full recovery in 2 to 4 weeks and may include fever, rash (including hives), arthralgia, myalgia, vasculitis, Arthus reaction, general ill feeling, itching, and swollen lymph nodes. Some of these findings, such as fever, rash, arthralgia, and myalgia are consistent with findings associated with IBD and may therefore be very difficult to assign to a particular etiology. When such a reaction is suspected,

samples for laboratory assessment will be obtained and stored. Tests will be performed if the diagnosis is confirmed and requested by the adjudication committee.

#### **8.1.4 Outcome Categorization**

The outcome of AEs must be recorded during the course of the study in the source document. Outcomes are as follows:

- Fatal
- Not Recovered/Not Resolved
- Recovered/Resolved
- Recovered/Resolved With Sequelae
- Recovering/Resolving
- Unknown.

#### **8.1.5 Symptoms of the Disease Under Study**

Symptoms of the disease under study should not be classed as AEs as long as they are within the normal day-to-day fluctuation or expected progression of the disease and are part of the efficacy data to be collected in the study; however, significant worsening of the symptoms should be recorded as an AE.

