The most common serious adverse events (SAEs) across all studies were CD and UC. In Study A7281006, the randomized, placebo-controlled induction study in CD, treatment-emergent adverse events (TEAEs) were most commonly reported within the GI disorders system organ class (SOC) followed by the infections and infestations SOC. The most common all-causality TEAEs were CD (worsening and progression of underlying disease), followed by pyrexia, headache, and arthralgia, all of which had similar incidences in the placebo treatment group compared with the active treatment groups. In Study A7281009, the randomized, placebo-controlled induction study in UC, TEAEs were most commonly reported within the GI disorders SOC followed by the infections and infestations SOC. The most common all-causality TEAE was headache, followed by abdominal pain, nasopharyngitis, UC (worsening and progression of underlying disease), and nausea, all with similar incidence between placebo- and drug-treated subjects.

The long-term, open-label safety studies (Studies A7281007 and A7281010) were not placebo-controlled, but permitted exposure to the investigational product at doses of 75 mg or 225 mg Q4W for 18 and 36 months, respectively. In Study A7281007, the most common all-causality TEAE was CD (worsening or progression), arthralgia, nasopharyngitis, and abdominal pain. In Study A7281010, the most common all-causality TEAEs were UC (worsening or progression), arthralgia, and nasopharyngitis.

Ontamalimab appears to be generally well tolerated, with the majority of TEAEs distributed at similar frequencies among treatment arms with only peripheral edema, gastroenteritis, and arthralgia more frequently reported in ontamalimab- than placebo-treated subjects in the pooled induction studies. In the placebo-controlled induction studies, nasopharyngitis was not reported more frequently in ontamalimab- than placebo-treated subjects, but occurred at relatively high frequency during long-term safety studies. Ontamalimab does not appear to be associated with impaired central nervous system (CNS) immune surveillance. No case of progressive multifocal leukoencephalopathy (PML) or myocarditis has been reported. Ontamalimab, in doses of 7.5 mg, 22.5 mg, and 75 mg, appears to increase the rate of remission in subjects with UC, and may have an effect in patients with CD who have greater evidence of inflammation based on biomarker or endoscopic data.

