### 7.3.3.11 Evaluation of Increased Gastrointestinal Symptoms

When a subject experiences an increase in GI symptoms, which could be an exacerbation of disease, an infectious etiology must be evaluated including testing for *C. difficile* as described in [Appendix 4](#). If the subject has undergone or is undergoing a glucocorticoid taper, the glucocorticoid dose should be increased to the pre-taper dose; when clinically stable, the taper may begin again per [Table 3](#).

Subjects should be assessed for possible treatment failure no earlier than the Week 4 scheduled visit. If treatment failure is considered after infectious etiology has been ruled out or treated, and/or after increase in the glucocorticoid dose (if appropriate), then the procedures in [Section 4.5.1.1](#) should be followed.

In each case, the appropriate AE (eg, infection, exacerbation) should be recorded in the subject's source document.

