7.1 Adverse Events

Adverse events will be coded using MedDRA Version 19.1 2016.

Treatment-emergent AEs (TEAEs) are defined as AEs with start dates at the time of or following the first exposure to IP in the SHP647-303 study.

An overall summary of the number of subjects with TEAEs will be presented, including the number and percentage of subjects with any TEAEs, serious TEAEs, TEAEs related to IP, related serious AEs (SAEs), TEAEs leading to discontinuation of IP, TEAEs leading to study discontinuation, and TEAEs leading to death.

The number of events, incidence, and percentage of subjects reporting TEAEs will be presented by treatment group as listed in Appendix 16.6; by preferred term; by SOC and preferred term; and by SOC, preferred term, and maximum severity. Treatment-emergent AEs considered related to IP will also be summarized by SOC and preferred term. If more than one AE occurs with the same preferred term for the same subject, then the

subject will be counted only once for that preferred term using the most severe and most related occurrence for the summarization by severity and by relationship to IP.

The most common TEAEs (incidence $\geq 2\%$ in any treatment group) will be summarized by preferred term in descending frequency by treatment group as listed in Appendix 16.6.

Serious TEAEs, TEAEs leading to discontinuation of the study or study medication, and injection site AEs will be summarized by SOC, preferred term, and treatment group as defined in Appendix 16.6. Adverse events leading to withdrawal, serious AEs, and deaths will be similarly summarized or listed.

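### Overall TEAE, serious TEAE and TEAE-discontinuation totals include recorded UC worsening, which is also the efficacy failure, and no total without it is planned

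*Protocol*

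**What the plan says.** **Recording.** Protocol 8.1.5: "Symptoms of the disease under study should not be classed as AEs as long as they are within the normal day-to-day fluctuation or expected progression" and are part of the efficacy data; however, "significant worsening of the symptoms should be recorded as an AE". It gives no criterion for significant. Protocol 7.3.3.11 starts lower: "When a subject experiences an increase in GI symptoms, which could be an exacerbation of disease, an infectious etiology must be evaluated". It ends: "In each case, the appropriate AE (eg, infection, exacerbation) should be recorded". Neither section refers to the other.

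**Analysis.** SAP 7.1: "An overall summary of the number of subjects with TEAEs will be presented, including the number and percentage of subjects with any TEAEs, serious TEAEs". The same list has rows for related TEAEs and related serious AEs, and for "TEAEs leading to discontinuation of IP, TEAEs leading to study discontinuation, and TEAEs leading to death". Protocol 9.9 plans overall TEAE counts in the same sense. Neither document removes UC terms from a total or adds a total without them. SAP 7.1 also tabulates TEAEs, serious TEAEs and TEAEs leading to discontinuation by system organ class and preferred term.

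**Related provisions.** Protocol 4.5.1 and 4.5.2 list treatment failure separately from adverse event as a reason for withdrawal. Under Protocol 3.1.3, treatment failures leave the study early. SAP 5.6 derives subject-years of exposure, but no AE rate uses them. On earlier studies Protocol 1.3 reports: "The most common serious adverse events (SAEs) across all studies were CD and UC".

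**The concern.** Subjects who responded to ontamalimab in induction are re-randomised to the same dose or to placebo, so relapse is what the efficacy analysis counts as failure. The sample-size premise (remission 38% on drug, 15% on placebo) already assumes unequal disease control. If relapse is recorded as an AE more often on placebo, the overall safety rows combine lack of efficacy in one arm with harm in the other.

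Those rows are what most readers look at first. A lower any-TEAE percentage on drug could then reflect fewer flares, while the share of subjects with some other event is higher. The preferred-term tables show the UC line but do not answer the obvious next question, namely how many subjects had any event other than UC worsening.

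**Working it through.** The plan states no AE, serious AE or discontinuation rate, so there is no figure of its own to reproduce. All rates below are assumptions, chosen to show a range.

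**Notation.** *u* is the risk of a UC-worsening AE and *h* the risk of any other AE; subscripts are P (placebo) and D (drug). If the two are independent within an arm, the total is T = 1 − (1 − u)(1 − h).

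**Worked cases** (difference is drug minus placebo)

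| Case | u_P, u_D | h_P, h_D | T_P | T_D | Difference in total | Difference without UC |
|---|---|---|---|---|---|---|
| Any TEAE, reversal | 30%, 15% | 40%, 45% | 1 − 0.70×0.60 = 58.0% | 1 − 0.85×0.55 = 53.25% | −4.75 | +5 |
| Any TEAE, no reversal | 10%, 5% | 40%, 45% | 1 − 0.90×0.60 = 46.0% | 1 − 0.95×0.55 = 47.75% | +1.75 | +5 |
| Serious, reversal | 6%, 3% | 3%, 5% | 1 − 0.94×0.97 = 8.82% | 1 − 0.97×0.95 = 7.85% | −0.97 | +2 |
| Serious, no reversal | 6%, 3% | 3%, 7% | 8.82% | 1 − 0.97×0.93 = 9.79% | +0.97 | +4 |

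**How much can be hidden.** Setting T_D = T_P gives the largest excess of other events on drug that the total conceals: (1 − h_P) × [1 − (1 − u_P)/(1 − u_D)].

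| u_P, u_D | h_P = 40% | h_P = 60% |
|---|---|---|
| 10%, 5% | 3.2 points | 2.1 points |
| 20%, 10% | 6.7 | 4.4 |
| 30%, 15% | 10.6 | 7.1 |
| 40%, 20% | 15.0 | 10.0 |

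**Equal UC worsening.** If u_P = u_D = u, the difference in totals is (1 − u)(h_D − h_P). It shrinks but keeps its sign.

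**Dependence on independence.** Take the first case again. If the two kinds of event overlap as far as possible, T is the larger of u and h: 40% against 45%, with no masking. If no subject has both, T = u + h: 70% against 60%, a difference of −10.

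**Why the preferred-term table does not settle it.** In the first case a reader sees, on placebo, any TEAE 58.0% and the UC line 30%. The share with any non-UC event then lies between 58.0 − 30 = 28.0% and 58.0%. On drug it lies between 53.25 − 15 = 38.25% and 53.25%. Drug minus placebo could be anything from 38.25 − 58.0 = −19.75 to 53.25 − 28.0 = +25.25 points, although the assumed truth is +5. The other preferred-term lines narrow these limits, but because subjects overlap between terms they do not give the count.

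**The case against.** - **The planned totals follow the AE definition.** Protocol 8.1 counts any untoward occurrence whatever its cause. This stands, and it is why the planned totals should stay.
- **UC worsening is not hidden.** It has its own preferred-term line. Named potential risks and adjudicated hypersensitivity are summarised separately (SAP 7.1.1), and AE listings would let a reader count subjects by hand. This also stands, but a hand count is not a planned summary and has no term list fixed in advance.
- **The related rows.** Protocol 8.1.2 treats an event readily explained by the underlying condition as not related, so ordinary relapse should largely drop out of them. They are a partial safeguard only: they also drop every other event judged unrelated.
- **The only controlled UC evidence in the documents points the other way.** Protocol 1.3 reports similar incidence of UC worsening on drug and placebo in the Phase 2 induction study. That study ran 12 weeks, and Protocol 2.1 says induction responses were not shown at Week 4 or 8. It says little about 52 weeks after re-randomisation, but a gap between arms here remains an assumption.
- **Early exit works against the masking.** Treatment failures leave early, which shortens the time for other events in the arm that relapses more and lowers its crude non-UC percentage. This is correct. A filtered crude percentage alone could therefore overstate a drug excess.

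A reader might also infer that Protocol 8.1.5 and 7.3.3.11 flatly contradict each other. The documents do not go that far: the two agree if an exacerbation is read as significant worsening. What remains is a difference in threshold for milder increases. Uneven recording between sites is possible, but nothing in the documents shows it.

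**Conclusion.** The gap is real and modest. SAP 7.1 and Protocol 9.9 plan no overall total without UC worsening, and the planned tables do not give the number of subjects with any non-UC event. If the drug prevents relapse, the totals can offset an excess of other events. With the halved UC rates above and 40% to 60% other events on placebo, the excess that can be concealed runs from 2.1 to 15.0 points. This rests on assumed rates and on independence.

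Two stronger readings are tempting but unsupported:

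- **That UC worsening sits in every discontinuation total.** Treatment failure is its own withdrawal reason and is tabulated under disposition (SAP 5.1). The documents leave open whether it also counts as a TEAE leading to discontinuation. Flares handled under Protocol 7.3.3.11 can still reach the any-TEAE row and, if serious, the serious row.
- **That an effective drug will look safer than placebo.** Reversal needs a sufficient gap in UC worsening between arms. Two of the four worked cases do not reverse, and none can under the independence model when UC worsening is equal.

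The point bears on how the safety totals are read. It does not affect the efficacy tests.

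**What to change.** 1. **SAP 7.1.** Beside the planned summary, repeat the rows for any TEAE, serious TEAE, and TEAE leading to discontinuation of investigational product or of the study, without a written list of UC-worsening preferred terms. Use the same treatment groupings (SAP Appendix 16.6). Fix the list before unblinding, which Protocol 6.2.4 ties to the unblinding of SHP647-304.
2. **Exposure.** Give both versions as rates per subject-year, using the exposure already derived in SAP 5.6. The TEAE definition has no end date and AEs are collected through follow-up, so count events over the same interval as the denominator.
3. **Treatment failure.** State in SAP 7.1 whether a treatment failure counts as a TEAE leading to discontinuation.
4. **Recording rule.** Reconcile the thresholds in Protocol 8.1.5 and 7.3.3.11. Table 2 of the protocol should not simply be imposed as the criterion: it must be met at two sequential visits, so it could miss a rapid flare, and it leaves lesser worsening undefined. With enrolment final at 366 and each subject's next visit becoming Week 52/ET under Amendment 3, a new recording rule would affect few data and could mix two standards. At minimum, the SAP should note the difference when the totals are interpreted.

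The cost is one or two extra tables and an agreed term list. Items 1 to 3 work on data already collected, and the planned totals stay.

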#### **8.1.6 Clinical Laboratory and Other Safety Evaluations**

A change in the value of a clinical laboratory, vital sign, or ECG assessment can represent an AE if the change is clinically relevant or if, during treatment with the investigational product, a shift of a parameter is observed from a normal value to an abnormal value, or a further worsening of an already abnormal value. When evaluating such changes, the extent of deviation from the reference range, the duration until return to the reference range, either while continuing treatment or after the end of treatment with the investigational product, and the range of variation of the respective parameter within its reference range, must be taken into consideration.

If, at the end of the treatment phase, there are abnormal clinical laboratory, vital sign, or ECG values which were not present at the pretreatment value observed closest to the start of study treatment, further investigations should be performed until the values return to within the reference range or until a plausible explanation (eg, concomitant disease) is found for the abnormal values.

The investigator should decide, based on the above criteria and the clinical condition of a subject, whether a change in a clinical laboratory, vital sign, or ECG parameter is clinically significant and therefore represents an AE.

### 8.1.7 Pregnancy

All pregnancies are to be reported from the time informed consent is signed until the end of the defined safety follow-up period stated in Section 7.2.3.

Any report of pregnancy for any female study participant or the partner of a male study participant must be reported within 24 hours to the Shire Global Drug Safety Department using the Shire Investigational and Marketed Products Pregnancy Report Form. A copy of the Shire Investigational and Marketed Products Pregnancy Report Form (and any applicable follow-up reports) must also be sent to the CRO/Shire medical monitor using the details specified in the [emergency contact information](#) section of the protocol. The pregnant female study participant must be withdrawn from the study.

Every effort should be made to gather information regarding the pregnancy outcome and condition of the infant. It is the responsibility of the investigator to obtain this information within 30 calendar days after the initial notification and approximately 30 calendar days postpartum. If the pregnancy outcome is a live birth, the vital status and clinical condition of the infant should be obtained and documented at 1 year postpartum.

Pregnancy complications such as spontaneous abortion/miscarriage or congenital abnormality are considered SAEs and must be reported using the Shire “Clinical Study Serious Adverse Event and Nonserious AE as Required by the Protocol Form.” Note: An elective abortion is not considered an SAE.

In addition to the above, if the investigator determines that the pregnancy meets serious criteria, it must be reported as an SAE using the Shire “Clinical Study Serious Adverse Event and Nonserious AE as Required by the Protocol Form” as well as the Shire Investigational and Marketed Products Pregnancy Report Form. The test date of the first positive serum/urine  $\beta$ -hCG test or ultrasound result will determine the pregnancy onset date.

